4 GENERAL STATISTICAL METHODS

4.1 Analysis Sets

Primary endpoint and selected secondary endpoints will be done for the following cohorts.

Enrolled Cohort

A subject is considered "enrolled" after signing the study-specific ICF. Subjects who sign the ICF but subsequently do not meet one or more of the selection criteria will be considered screen failures and excluded from the study.

Intent-to-Treat Cohort (ITT)

This cohort consists of those "enrolled" subjects who meet all inclusion/exclusion criteria and are subsequently randomized. Subjects in this cohort who do not receive a study stent(s) will be counted towards the enrollment ceiling. Any adverse events occurring or resulting from a treatment attempt will be collected. Protocol deviations will be collected as necessary.

Per-Protocol Cohort (PP)

The per-protocol cohort is a subset of the ITT subjects who receive the study stent(s) as randomized and no major protocol deviations (Per ICH E9).

5 ADDITIONAL DATA ANALYSES

5.1 Secondary Endpoints

- 1. Occurrence of adverse events related to the stent and/or the stent placement or removal procedures
- 2. Number of ERCP procedures through 24 months after initial stent placement
- 3. Ability to deploy the stent(s) in satisfactory position
- 4. Stent Removal:

Version AA March 20, 2013 Boston Scientific WallFlex Biliary FC CP RCT SAP 90913894/Ver. AA Page 10 of 13

- a. Ability to remove the stent(s) without serious stent removal related adverse events at each procedure involving removal of stent(s) (technical success at removal) or
- b. Complete distal migration without serious stent removal related adverse events
- 5. Liver Function Tests (LFT's)
 - a. LFT improvement at month 1 compared to baseline naïve stricture or to LFTs at time of plastic stent placement 6 months or fewer prior to enrollment in strictures treated with 1 prior plastic stent.
 - b. LFTs at month 24 compared to removal of last stent (applicable for subjects who had not been re-stented at time of month 24 visit)
- 6. Health Economic Endpoints:
 - Number of outpatient procedures
 - Number of hospitalizations
 - o Duration of hospitalizations
 - Length of procedures

The secondary endpoints will be summarized using descriptive statistics (mean, standard deviation, n, minimum, maximum) for continuous variables and frequency statistics for discrete variables. Statistical testing will be performed using appropriate methods. For analysis of LFT's, McNemar's Test or repeated measures regression model may be used.

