4.2. Secondary Endpoints

1. Occurrence of adverse events related to the stent and/or the stent placement or removal procedures
2. Number of ERCP procedures through 24 months after initial stent placement
3. Ability to deploy the stent(s) in satisfactory position
4. Stent Removal:
 - Ability to remove the stent(s) without serious stent removal related adverse events at each procedure involving removal of stent(s) (technical success at removal) or
 - Complete distal migration without serious stent removal related adverse events
5. Liver Function Tests (LFT's)
 - Baseline LFTs compared to LFTs taken at time of original plastic stent placement for any subject with a prior plastic stent
 - LFT improvement at 1 month post-study treatment compared to baseline LFTs (and/or compared to LFTs taken at time of original plastic stent placement for any subject with a prior plastic stent)
 - LFTs at month 24 compared to LFTs at removal of last stent (applicable for subjects who had not been re-stented at time of month 24 visit)
6. Health Economic Endpoints:
 - Number of outpatient procedures
 - Number of hospitalizations
 - Duration of hospitalizations

- Length of procedures
- Number of devices

5. Design

The study is designed as a post-market, multi-center, prospective, non-blinded, randomized study. At least 164 subjects (82 per arm) will be treated with 1:1 randomization between Group A and Group B and will be followed through 24 months post-initial stent(s) placement:

- Subjects in the MS arm will be treated with a single metal stent, which will be removed 12 months post-placement.
- Subjects in the PS arm will receive 2 plastic stents when possible. Subjects in this arm will undergo plastic stents exchange/bile duct calibration at 4 and 8 month post-initial stent placement. At each stent exchange, the goal should be to provide progressive stent therapy by increasing the number of plastic stents at 4 months and again at 8 months. Final plastic stent removal will occur 12 months post-initial stent placement.

5.1. Inclusion Criteria:

- Age 18 or older
- Willing and able to comply with the study procedures and provide written informed consent to participate in the study
- Chronic pancreatitis

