The schedule of observations and assessments to take place during the study follows on the next page.

Table 1. Study Event Schedule

Study Visit	Screening/ Baseline	Treatment	Mo. 1* (30 d)	Mo. 4 (120 d)	Mo. 8 (240 d)	Mo. 11-12 (330-360 d)	Mo 24* (720 d)	Additional ERCP
Window	≤ 5 days prior to treatment	N/A	±10 d	±30 d	±30 d	See range above	±30 d	NA
ICF	X							
Eligibility Assessment	X							
Demographics	X							
Medical History	X							
Liver Function Normal Ranges	X**						X	X****
Liver Function Tests	X		X	***	***	X	X	X
Assessment of Biliary Obstructive Symptoms	X		X			X	X	X****
Randomization		X						
Stent Placement/Exchange		X		PS Only	PS Only			X (if done)
Stent Removal						X		
Cholangiogram or other Common Bile Duct Imaging	X (prior to stent placement)					X (after stent removal)		X (if standard of practice)
AE/Device Malfunction Assessment	Report as occurs/needed per the Protocol Reporting Requirements – See Section 11.							
Protocol Deviations	Report as occurs/needed.							

*Visit may be conducted in the office or via telephone with liver function tests drawn and sent from local clinic/hospital.

**In addition to baseline LFTs, LFTs are also to be collected from time of original plastic stent placement for any subject with a prior plastic stent.

***If subject is not re-stented after Month 4 or 8 Plastic Stent Exchange, Liver Function Tests must be collected at that visit.

****Required for any visit that results in re-stenting

7.2. *Study Candidate Screening*

No study-specific testing will be conducted until after the subject has signed an ICF. A Screen Failure/Enrolled Log will be maintained in EDC by the center to document select information about candidates who signed consent.

7.3. *Informed Consent*

Written Informed Consent must be obtained for all subjects who are potential study candidates. Subjects will be asked to sign the Informed Consent form before any study-specific tests or procedures are performed. The Informed Consent form is study-specific and must be approved by the study Institutional Review Board (IRB)/Ethics Committee (EC). Study personnel should explain that even if a subject agrees to participate in the study and signs the ICF, the ERCP procedure may demonstrate that the subject is not a suitable candidate for the study.

7.4. *Study Visits*

7.4.1. **Screening/Baseline – Visits/Assessments must occur within 5 days prior to stent placement – Office Visit**

- Informed Consent (See Section 7.3)

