- Eligibility Criteria Assessment
- Demographics
- Medical History
- Collection of Liver Function Normal Ranges
- Liver Function Tests (at enrollment for naïve strictures or at the time of prior plastic stent placement in strictures that had one prior plastic stent inserted)
 - Alkaline phosphatase – mandatory
 - Total Bilirubin – mandatory
 - Gamma GT – optional
 - SGOT and SGPT (AST, ALT) – optional
- Assessment of Biliary Obstructive Symptoms
 - Right Upper Quadrant Pain
 - Fever/Chills
 - Jaundice
 - Itching
 - Dark urine
 - Pale stools
 - Nausea/Vomiting
- Cholangiogram or other Common Bile Duct Imaging
- Adverse Event/Device Malfunction Assessment

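### For previously stented subjects, SAP 5.1 item 5a measures month-1 LFT improvement only from the earlier plastic stent, so the within-arm figure can include change that preceded study treatment (minor)

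*SAP*

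**What the plan says.** SAP 5.1 item 5a defines one endpoint with two reference points. It reads "LFT improvement at month 1 compared to baseline naïve stricture or to LFTs at time of plastic stent placement", and the second reference is fully specified as "to LFTs at time of plastic stent placement 6 months or fewer prior to enrollment in strictures treated with 1 prior plastic stent". No comparison with enrolment baseline is listed for previously stented subjects. The section allows McNemar's test or a repeated measures regression for LFTs. SAP 5.3 plans subgroup analyses by gender only, so no split by prior stenting is prespecified.

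Protocol 4.2 item 5, repeated in the synopsis, is broader:

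- Its month-1 endpoint begins "LFT improvement at 1 month post-study treatment compared to baseline LFTs" and continues in brackets "and/or compared to LFTs taken at time of original plastic stent placement for any subject with a prior plastic stent".
- It has a further LFT endpoint, "Baseline LFTs compared to LFTs taken at time of original plastic stent placement for any subject with a prior plastic stent", which SAP 5.1 does not carry.

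On data collection the protocol is not uniform. Table 1 marks LFTs at Screening/Baseline, and its footnote says "In addition to baseline LFTs, LFTs are also to be collected from time of original plastic stent placement", so two values are expected. Section 7.4.1 describes the screening LFTs as those at enrolment for naïve strictures "or at the time of prior plastic stent placement in strictures that had one prior plastic stent inserted", which reads as one value or the other.

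**The concern.** A previously stented subject enters the trial after a period of drainage. A change measured from before that drainage mixes what the earlier stent did with what the study stent did. The reference value is also taken at the point where, under the inclusion criteria, such a subject's symptomatic stricture is documented, so it tends to be a poor one.

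The planned methods work within subjects. Under McNemar's test, someone with abnormal LFTs before the first stent who was already normal at enrolment would count as improved at month 1, even if the study stent changed nothing.

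What is at stake is how the within-arm improvement at month 1 is read. A second, practical risk is that a site following 7.4.1 literally might not draw an enrolment sample in this group, and that value could not be recovered later.

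**Working it through.** The documents state no effect size, sample size or power for this endpoint, so there is no planned figure to reproduce. The check compares the texts and then works through the arithmetic of the change score.

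**Comparisons listed for previously stented subjects**

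| Comparison | Protocol 4.2 item 5 | SAP 5.1 item 5 |
|---|---|---|
| Month 1 against enrolment baseline | Yes, named first | Not listed |
| Month 1 against original placement | Yes, by *and/or* | Yes, the only month-1 comparison |
| Baseline against original placement | Yes, separate endpoint | Not listed |

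**What the SAP change contains.** Let O be the value at original placement, B the enrolment baseline and M the month-1 value. Then

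O − M = (O − B) + (B − M).

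Only B − M follows the study stent. The share that precedes it is (O − B) / (O − M).

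**Illustration for one subject.** Alkaline phosphatase is in multiples of normal. O = 3.0 is the threshold of the alkaline phosphatase route into the trial; subjects may also qualify by cholangitis or jaundice. The values of M and B are assumptions.

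| M | B | O − M (SAP) | B − M | Share before study stent |
|---|---|---|---|---|
| 1.0 | 1.0 | 2.0 | 0 | 100% |
| 1.0 | 1.5 | 2.0 | 0.5 | 75% |
| 1.0 | 2.0 | 2.0 | 1.0 | 50% |
| 1.0 | 2.5 | 2.0 | 1.5 | 25% |
| 1.0 | 3.0 | 2.0 | 2.0 | 0% |
| 1.5 | 1.5 | 1.5 | 0 | 100% |
| 1.5 | 2.0 | 1.5 | 0.5 | 67% |
| 1.5 | 2.5 | 1.5 | 1.0 | 33% |
| 1.5 | 3.0 | 1.5 | 1.5 | 0% |

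For a given M the SAP change is constant down the column. It cannot distinguish a study stent that did everything from one that did nothing.

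**Effect on the pooled mean.** Let p be the share of previously stented subjects, f their relative fall from O to B, and s the relative fall from B to M, taken as equal across these subjects for simplicity. Relative improvement from O is 1 − (1 − f)(1 − s); from B it is s. The difference is f(1 − s), so the pooled excess is p × f × (1 − s). All three inputs are assumptions:

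- p = 0.2, f = 0.3, s = 0: 0.2 × 0.3 × 1 = 0.06, or 6 points.
- p = 0.5, f = 0.5, s = 0: 0.5 × 0.5 × 1 = 0.25, or 25 points.
- The same two cases with s = 0.5: 0.06 × 0.5 = 0.03 and 0.25 × 0.5 = 0.125, or 3 and 12.5 points.
- f = 0, for example if the earlier stent had stopped working by enrolment: 0 points.

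**Between arms.** O and B are both fixed before the study stent is placed. Under the 1:1 randomisation of protocol 7.4.2 the mean of O − B is expected to be the same in both arms, so on the absolute-change scale it cancels in expectation. Randomisation is stratified by site and not by prior stenting, so chance imbalance and extra variance remain.

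**The case against.** The strongest defence is that the SAP uses a reference the protocol allows. The bracketed *and/or* in protocol 4.2 item 5 makes original placement an acceptable comparator for previously stented subjects. Section 7.4.1 goes further and lists the prior-placement LFTs under the baseline visit for this group. Measuring everyone from the undrained state that qualified them is a coherent question, though a different one. This stands: a reader might infer that the SAP contradicts the protocol, but the SAP narrows the protocol to one of its permitted options.

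A reader might also infer that the comparison of metal with plastic stents is biased. Randomisation gives no reason to expect that, as shown above.

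A third tempting reading is that previously stented subjects will have no enrolment LFTs. Table 1 and its footnote ask for both values, and the baseline-against-original endpoint cannot be computed without both. What remains is conflicting wording in 7.4.1.

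Two further limits apply. The LFT list in the SAP's own synopsis is not in the text available for this review, so the point is confined to SAP 5.1. And SAP section 2 cites protocol Version AB of 17 January 2012, whereas the supplied protocol carries the date February 15, 2013. An older source text could explain the mismatch, but the documents do not say so.

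None of this answers the remaining point: within SAP 5.1, the month-1 change for this group cannot be separated into its two parts.

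**Conclusion.** The point holds in a limited form and is minor. SAP 5.1 item 5a keeps only the original-placement comparison for previously stented subjects and omits the protocol endpoint that would separate the earlier stent's effect from the study stent's. The within-arm improvement can therefore include change that preceded study treatment.

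Its size cannot be fixed from the documents. For a single subject the share runs from 0% to 100% as the enrolment value varies between the month-1 value and the original-placement value. For the pooled mean the excess runs from zero to 25 percentage points under the assumed inputs, and the upper end needs half the subjects previously stented, a 50% earlier fall and no study-stent effect in them.

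The primary endpoint is unaffected, because it refers alkaline phosphatase to the level at the end of the stenting period. The LFT endpoint is secondary and has no stated power or decision rule.

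**What to change.** Align SAP 5.1 item 5 with protocol 4.2 item 5 by listing three comparisons:

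1. Month 1 against enrolment baseline, for all subjects. Adjust any between-arm comparison for the enrolment value; SAP 3.1.3 already provides for analysis of covariance.
2. Month 1 against original placement, for previously stented subjects only, reported separately and labelled as spanning both stents.
3. Enrolment baseline against original placement, for previously stented subjects.

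In the protocol, reconcile 7.4.1 with the Table 1 footnote so that it is clear both values are collected in previously stented subjects. When the SAP is revised, check the protocol version it cites.

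The cost is a few lines in the SAP and one in the protocol. Table 1 already calls for both values, so no assessment is added.

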5.2 Interim Analysis

Informal Interim Analysis once the first 50 subjects have reached 24 months post initial stent placement. This analysis will consist of the primary and some or all of the secondary endpoints and demographics if deemed necessary. This analysis will consist of only descriptive statistics (mean, standard deviation, n, minimum, maximum) for continuous variables and frequency statistics for discrete variables. There will be no testing done for this interim analysis.

5.3 Subgroup Analyses

The subgroup analyses will include analyzing the primary endpoint and select secondary endpoints by gender.

5.4 Justification of Pooling

The analyses will be presented using pooled data across institutions. An analysis of the poolability will be made using logistic regression for binary outcomes, proportional hazards regression for time-to-event outcomes, or analysis of variance for continuous outcomes, to assess differences between study institutions and to justify pooling data across institutions.

Version AA March 20, 2013 Boston Scientific WallFlex Biliary FC CP RCT SAP 90913894/Ver. AA Page 11 of 13

5.5 Multivariable Analysis

Univariate and multivariate analyses will be performed to assess possible predictors of the stricture resolution, removability of stents, and distal migration. Possible predictors may include any but not limited to demographic/baseline data and medical history data. Factors from the univariate model with p \leq 0.20 will also be modeled multivariately using a stepwise procedure in a logistic regression model or Cox proportional hazards regression model. The significance thresholds for entry and exit into the model will be set to p<0.10.

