3.1.2 Sample Size

A literature search of metal and or plastic stenting for treatment of benign biliary strictures secondary to chronic pancreatitis yielded 4 articles representing 70 subjects treated with metal stenting (MS)²⁻⁷ and 3 articles representing 60 subjects treated with plastic stenting (PS)⁸⁻¹³.

The following meta-analysis was conducted of the probability of stricture resolution:

- Metal Stenting: A meta-analysis of the stricture resolution rate during the reported follow-up after initial stent placement yields a proportion of 0.762 [95% CI: 0.593 0.895]²⁻⁷.
- Plastic Stenting: A meta-analysis of the stricture resolution rate during the reported follow-up after initial stent placement yields a proportion of 0.611 [95% CI: 0.311 0.870] ⁸⁻¹³.

The sample size was calculated for a one-sided 0.050 Farrington-Manning test using SAS 9.2®. If the P value from the Farrington-Manning test is <0.05 then the metal stent group will be considered non-inferior to the plastic stent group. The expected probability of a stricture resolution in the metal stent arm and plastic stent arm is 66.0%, which was taken from the 95% CIs from the meta-analysis above. The non-inferiority margin (Δ) is 20%. Given these assumptions, and a one-sided 5% significance level, 2 x 74 = 148 subjects will provide 80% power to reject the null hypothesis, that the metal stent group is inferior to the plastic stent group. To compensate for possible loss of subjects between enrollment and complete assessment of inclusion/exclusion criteria and subsequent randomization, an additional 10% of subjects will be enrolled for a total of 2 x 82 = 164.

Version AA March 20, 2013 Boston Scientific WallFlex Biliary FC CP RCT SAP 90913894/Ver. AA Page 8 of 13

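### SAP 5.5 picks predictors by p-value from an open list without forcing in stent arm, so it will often report false predictors, with p-values and intervals that are not valid after selection

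*SAP*

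**What the plan says.** SAP 5.5 (Multivariable Analysis) sets out univariate and multivariate analyses to "assess possible predictors of the stricture resolution, removability of stents, and distal migration". The candidates are left open: "Possible predictors may include any but not limited to demographic/baseline data and medical history data". Factors reaching a univariate p-value of 0.20 or less "will also be modeled multivariately using a stepwise procedure in a logistic regression model or Cox proportional hazards regression model", and "The significance thresholds for entry and exit into the model will be set to p<0.10".

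The section gives no list or maximum number of candidates. It does not require stent arm in the model, and it mentions no shrinkage, internal validation or multiplicity control. It sits under SAP 5 (Additional Data Analyses), but the results are not labelled exploratory.

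The confirmatory analysis is elsewhere. SAP 3.1.2 sizes the trial for a non-inferiority test ("The sample size was calculated for a one-sided 0.050 Farrington-Manning test using SAS 9.2"), and SAP 7.3 repeats that test and adds between-arm tests for removability, adverse events and number of ERCP procedures.

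**The concern.** Stepwise selection tests many factors and reports the survivors as if each had been the only one tested. With an open list, an entry threshold of 0.10 and three outcomes, some survivors are likely to be chance findings. Their p-values and intervals do not reflect the search that produced them.

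Stent arm is the one factor the trial randomises, and here it has to compete for entry like any other. A migration model that leaves it out would be hard to interpret in a metal-versus-plastic trial.

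At stake are the secondary statements about which patients resolve, whose stent can be removed and whose stent migrates. SAP 2 allows the specified analyses to be used in presentations and manuscripts, so these statements may be published.

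**Working it through.** **Plan's own figure.** The documents give no false-predictor rate for SAP 5.5, so there is none to reproduce.

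**Inputs from the documents**
- Thresholds: 0.20 for screening, 0.10 for entry and exit (SAP 5.5).
- Sample size: "2 x 74 = 148 subjects will provide 80% power to reject the null hypothesis", and "an additional 10% of subjects will be enrolled for a total of 2 x 82 = 164" (SAP 3.1.2).
- Expected resolution: 66% in both arms (SAP 3.1.2), so 0.34 x 148 = about 50 non-resolutions.
- Literature migration rates: plastic 10.2-13% (Protocol 1.2), metal 5-16.2% (Protocol 1.3). Over the widest range, 0.05 x 148 = about 7 to 0.162 x 148 = about 24 events.

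**Assumptions**
- The number of candidates k is not given, so a range is shown. For a reference value, Protocol 7.4.1 lists seven obstructive symptoms and two mandatory liver tests, the entry criteria add age and prior plastic stent, and SAP 5.3 names gender: 7 + 2 + 2 + 1 = 12, before medical history and the optional tests.
- Every candidate is null.
- Removability is taken as 90% (no rate is given) and migration as 10%.

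**False predictors.** A null candidate passes the 0.10 threshold with probability 0.10. For k independent candidates,

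P(at least one kept) = 1 - 0.9^k.

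The full SAP 5.5 procedure was also simulated (logistic models, n = 148, 400-1000 runs per cell; 600 at k = 12).

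| k | 1 - 0.9^k | Simulated, resolution alone | Simulated, at least one of three outcomes |
|---|---|---|---|
| 3 | 27% | 27% | 60% |
| 6 | 47% | 45% | 83% |
| 7 | 52% | 53% | 87% |
| 10 | 65% | 62% (65% in a second simulation) | 94% |
| 12 | 72% | 71% | not run |
| 15 | 79% | 80% | 99% |
| 20 | 88% | 86-87% | 100% |

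The last column treats the three outcomes as independent. Removability and migration probably are not, so it is an upper guide.

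**What drives the rate**
- Correlation: with candidates correlated at 0.3, resolution alone gives 61% (k = 10), 68% (k = 12) and 73% (k = 15).
- Trial size: at k = 10 the rate is 62% at both n = 148 and n = 164.
- Event count: about 50 and about 15 events give almost the same rates (62%, 80%, 86% against 62%, 80%, 87% for k = 10, 15, 20).
- The 0.20 screen adds almost nothing, because the 0.10 threshold is stricter.

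**Why the reported p-values fail.** A null p-value is uniform. Given that a null candidate was kept because p<0.10, the chance that it shows p<0.05 is about 0.05/0.10 = 50%, not 5%. In the simulations at least one false predictor of resolution had p<0.05 in 42% of trials at k = 10 and 47% at k = 12.

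**Stent arm.** Take migration at 5% with metal and 13% with plastic, both inside the literature ranges, with 74 per arm.
- Log odds ratio = ln[(0.13/0.87)/(0.05/0.95)] = 1.04.
- Standard error = sqrt[1/(74 x 0.13 x 0.87) + 1/(74 x 0.05 x 0.95)] = sqrt(0.119 + 0.285) = 0.64.
- z = 1.04/0.64 = about 1.64, against a two-sided 0.10 critical value of 1.645, so arm enters about 50% of the time.

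Simulation of the SAP procedure kept arm in 46% of trials. The two agree that arm would be left out about half the time even with a difference of this size.

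**Sparse outcomes.** With 12 candidates, 7 to 24 migrations leave 7/12 = 0.6 to 24/12 = 2 events per candidate. That is too few for unpenalised stepwise modelling to give stable estimates.

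**The case against.** The strongest reply is that the number of candidates is unknown, so no single false-predictor rate can be attached to this plan. That stands. A reader might infer that most trials of this size would report false predictors of all three outcomes. The documents do not support that. For resolution alone, a majority needs 7 or more null candidates; for all three outcomes at once, (1 - 0.9^k)^3 exceeds one half only from about k = 15 (0.794^3 = 0.50). Neither the 148 subjects nor the small number of migrations is the cause.

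A reader might also infer that the selected models would be mostly noise. That was not shown: every simulated candidate was null by construction, and real predictors may exist.

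It is also fair to say that the between-arm conclusions do not rest on SAP 5.5. The tests in SAP 7.3 do not use the selected model, and SAP 3.1.3 reports safety and effectiveness by arm with covariate adjustment. Section 5.5 specifies no treatment interactions, so it is a prognostic search and does not estimate who benefits from which stent. Nor do the documents establish that all three outcomes depend on stent type: resolution is assumed equal in both arms, and the literature migration ranges overlap. Those ranges also cover migration in all subjects of the cited studies, including other strictures and other stent designs, so the 5% and 13% above are illustrative only.

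What remains is that the rule as written has no safeguard, and an analyst who follows it with a dozen candidates would probably report something false.

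**Conclusion.** The point holds as a cheap improvement to a secondary analysis. The selection rule in SAP 5.5 will often report false predictors, and its post-selection p-values and confidence intervals are not valid. If nothing is truly predictive, the chance of at least one false predictor of resolution is about 62-65% with 10 candidates and about 71% with 12, and below 50% with 6 or fewer. These figures rest on an assumed candidate count and on all candidates being null; moderate correlation lowers them somewhat. The main drivers are the number of candidates and the 0.10 threshold.

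Leaving arm unforced is a separate weakness. With illustrative migration rates of 5% and 13%, arm would be kept in about 46-50% of trials. Nothing here touches the primary non-inferiority conclusion or the between-arm tests in SAP 7.3.

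**What to change.** Replace the selection procedure in SAP 5.5.

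- **Resolution:** fit one logistic model with stent arm forced in and a short list of baseline covariates named now, with no p-value selection. Up to four is a reasonable cap: arm plus four is five terms, and 50/5 = about 10 expected non-resolutions per term. Prior plastic stent and baseline alkaline phosphatase are possible members.
- **Removability and migration:** force arm in and use Firth-penalised logistic regression with the same capped list. The cap matters because Firth's method deals with small-sample bias and separation, not with multiplicity; trying an unlimited number of candidates one at a time would bring the problem back. With 7 to 24 migrations over five terms (about 1.5 to 5 per term) the intervals will be wide, and the report should say so.
- **Reporting:** give every estimate with its confidence interval, whether or not it is significant, and label the section exploratory.

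The same list could serve the covariate-adjusted analyses in SAP 3.1.3, which do not name their covariates. The change needs SAP wording only, approved before the analyses as SAP 5.6 provides, and it reduces the analysis work. The cost is that fewer factors are explored.
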